2. Determine whether once daily dosing of ferrous sulfate 325mg has a lower side effect profile than twice daily dosing.
3. Determine the relationship between frequency of maternal iron administration and maternal hepcidin
4. Determine the relationship between frequency of maternal iron administration and fetal iron stores

Secondary Aim

Determine whether once daily dosing of ferrous sulfate 325mg is associated with a lower rate of maternal blood transfusion at the time of delivery than twice daily dosing.

Inclusion Criteria

Singleton gestation in the second trimester (14-28 weeks) who is not on iron therapy and has a normal hemoglobin electrophoresis if from a high risk group for hemoglobinopathy.

Exclusion Criteria

Multiple gestation, maternal hemoglobinopathy or hemochromatosis, subjects with irritable bowel disease or irritable bowel syndrome, history of bariatric surgery or extensive bowel surgery, or individuals already receiving iron supplementation aside from prenatal vitamins.

Study Design

[figure not shown]

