This will be a prospective, randomized, double blinded placebo controlled clinical trial. Subjects will be identified for possible enrollment during the second trimester during routine prenatal care. Criteria for enrollment will be a singleton intrauterine gestation as above. Subjects without anemia will have weekly questionnaires regarding GI symptoms during otherwise scheduled prenatal visits. Subjects with iron deficiency anemia as diagnosed by an Hgb concentration of less than 10.5-11mg/dL per ACOG guidelines and a ferritin of less than 15mg/dL will be randomized to once or twice daily iron supplementation by means of a computer generated random number list by the investigational drug pharmacy. The study drug will be provided by the University of Missouri Investigational Drug Pharmacy under the guidance of [name], the Investigational Drug Pharmacist for the University. Iron supplementation will be in the form of ferrous sulfate 325mg (65mg of elemental iron) once or twice daily. Anemic subjects will receive identical packs of drug with instructions to take one pill BID (twice daily). The morning pill will be ferrous sulfate 325mg. The evening pill will be randomized to contain either ferrous sulfate 325mg or placebo. The placebo will be produced by the investigational drug pharmacy and contain cellulose, a biologically inert plant fiber. The subjects and investigators will be blinded to assignment. As part of standard Obstetric care, the subject will have a hemoglobin repeated at the time of admission to labor and delivery and on post-partum day 1. Subjects who are not anemic will serve as controls and not receive a prescription. This is appropriate as the standard of care is not to treat non-anemic women with iron supplementation.

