- The type and timing of the data to be collected for withdrawn subjects.
All data collected from a withdrawn subject will immediately be destroyed.
- Whether and how subjects are to be replaced.
To replace withdrawn subjects, we will recruit another pregnant mother
- The follow-up for subjects withdrawn from investigational product treatment/trial treatment.
There will be no follow-up.

Data handling:

All data will be coded with an ID number. The key containing the ID numbers will be kept in a locked file separate from the data. Data generated from samples tested for this study will be stored by the MU Biorepository and by the research staff. . The data will be kept for 7 years after study completion. This data will not be shared with outside investigators or used for research other than this study. Additionally, data from this study will be included in the Prospective Obstetric Database (PODS) study for future use in de-identified fashion.

Data Analysis

Statistical Analysis: Statistical analyses will be performed using the IBM SPSS statistical software version 22 (IBM Corporation, Armonk, NY, USA). ANOVA will be used to assess the difference in mean hemoglobin at the time of admission and post-partum in the three arms for the study. Regression analysis will be used to explore the relationships of iron supplementation on maternal hemoglobin at delivery and fetal hemoglobin, hepcidin, and ferritin while controlling for maternal ferritin and hepcidin at enrollment. A planned secondary analysis will be to use a Chi-square or Fisher's exact test as appropriate to examine the incidence of blood transfusion during the admission for delivery. Significance will be set at $P \leq 0.05$.

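### The exploratory regression on iron supplementation is not limited to randomised women and omits enrollment hemoglobin; if the untreated controls enter under a yes/no or dose coding, its hemoglobin coefficient is biased against iron

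*Combined protocol and SAP*

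**What the plan says.** **Who receives iron (Study Design).** The women randomised are "Subjects with iron deficiency anemia as diagnosed by an Hgb concentration of less than 10.5-11mg/dL per ACOG guidelines and a ferritin of less than 15mg/dL". Both randomised arms take iron in the morning, and only the second pill differs: "The evening pill will be randomized to contain either ferrous sulfate 325mg or placebo". The comparison group is neither randomised nor treated: "Subjects who are not anemic will serve as controls and not receive a prescription".

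**What is analysed (Data Analysis, Statistical Analysis).** Hemoglobin at admission and post-partum is compared by ANOVA "in the three arms for the study", so the controls are in that test. The next sentence reads "Regression analysis will be used to explore the relationships of iron supplementation on maternal hemoglobin at delivery and fetal hemoglobin, hepcidin, and ferritin". Its adjustment set is given by the closing words, "while controlling for maternal ferritin and hepcidin at enrollment". It does not say who enters the model or how supplementation is coded, and enrollment hemoglobin is not a listed covariate.

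**What the model has to answer (Specific Aims).** Aim 4 is "Determine the relationship between frequency of maternal iron administration and fetal iron stores". This regression is the only stated analysis of the fetal outcomes and the only adjusted analysis of delivery hemoglobin.

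**The concern.** Randomisation decides once versus twice daily. It does not decide iron versus no iron, which follows from enrollment hemoglobin and ferritin. A coefficient for iron versus none can therefore come only from comparing women selected for low hemoglobin with women selected for not having it. The variable that drives that selection is missing from the covariates.

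Women who start lower tend to finish lower, so part of the starting deficit is charged to iron. The result would look like an adjusted treatment effect while resting on a contrast that nobody randomised, and effective iron could appear useless. In addition, Aim 4 concerns frequency, and a yes/no supplementation term would not estimate it.

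**Working it through.** **1. The plan's own figure.** Power Analysis gives 17 per arm for a difference of 1, SD 1, alpha 0.05 and 80% power. An exact two-sided two-sample t-test has power 0.781 at n = 16 and 0.807 at n = 17, so 17 reproduces. The regression issue does not touch it.

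**2. Starting gap.** Inputs: hemoglobin mean 12 and SD 1 (Power Analysis, plan's units), and a cut-off c of 10.5 or 11 (Study Design). With z = c - 12, φ the normal density and Φ the normal distribution function, the mean below the cut-off is 12 - φ(z)/Φ(z), and the mean above it is 12 + φ(z)/(1 - Φ(z)).

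| Cut-off | Mean below | Mean above | Gap |
|---|---|---|---|
| 10.5 | 10.06 | 12.14 | 2.08 |
| 11 | 10.47 | 12.29 | 1.81 |

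**3. Bias with no adjustment.** Let b be the slope of delivery hemoglobin on enrollment hemoglobin (tracking). The bias of a yes/no term is about -b × gap. A true +1.0 is cancelled at b = 1/2.08 = 0.48 (cut-off 10.5) or 1/1.81 = 0.55 (cut-off 11).

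**4. Bias with the planned covariates.** This step needs values that the documents do not give. Assumed:
- tracking b of 0.3 to 0.7;
- hemoglobin-ferritin correlation of 0.2 to 0.5;
- log-normal ferritin, median 25 and log SD 0.7;
- correlation of log ferritin with log hepcidin of 0.6.

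Treated women have hemoglobin below the cut-off and ferritin below 15; controls have hemoglobin at or above the cut-off; the ratio is 1:4. Simulated least-squares fits on treatment, ferritin and hepcidin put a true +1.0 at about -0.4 (cut-off 10.5, correlation 0.2, b = 0.7) to +0.6 (cut-off 11, correlation 0.5, b = 0.3). Every cell is too low. The bias does not depend on the true effect, so a true +0.5 shifts the range down by 0.5, to about -0.9 to +0.1.

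**5. At the planned size.** Model with the planned covariates, yes/no term, true effect +1.0, 50 treated and 200 controls. The correlation of 0.6 goes beyond the range in step 4 and favours the plan.

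| Cut-off | Correlation | b | Mean estimate | 95% CI covers +1.0 | Significant benefit | Significant harm |
|---|---|---|---|---|---|---|
| 10.5 | 0.3 | 0.5 | 0.10 | 0.0% | 7.4% | 0.6% |
| 10.5 | 0.3 | 0.7 | -0.26 | 0.0% | 0.0% | 30.6% |
| 10.5 | 0.6 | 0.5 | 0.33 | 4.4% | 41.8% | 0.0% |
| 10.5 | 0.6 | 0.7 | 0.06 | 0.0% | 4.4% | 0.6% |
| 11 | 0.3 | 0.5 | 0.20 | 0.4% | 19.9% | 0.0% |
| 11 | 0.3 | 0.7 | -0.13 | 0.0% | 0.3% | 10.3% |
| 11 | 0.6 | 0.5 | 0.39 | 9.5% | 55.8% | 0.0% |
| 11 | 0.6 | 0.7 | 0.15 | 0.0% | 13.8% | 0.1% |

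**6. Other codings and models.**
- *0/1/2 doses with controls.* Let the true steps be 1.0 (none to once) and 0.5 (once to twice), with groups of 200, 25 and 25. Ignoring covariates, the unconfounded slope is Sxy/Sxx. Mean x = 75/250 = 0.3 and mean y = (25 × 1 + 25 × 1.5)/250 = 0.25. Sxy = 25 + 75 - 250 × 0.3 × 0.25 = 81.25, and Sxx = 25 + 100 - 250 × 0.09 = 102.5, so the slope is 0.79. The simulated slope is -0.03 to 0.58 over correlations of 0 to 0.6, again too low.
- *Three-level factor with controls, read for twice versus once.* A true 0.5 is recovered as 0.48 to 0.52.
- *Enrollment hemoglobin added, yes/no term.* A true 1.0 is recovered as 0.99 to 1.01, because the simulated relation is linear.
- *Randomised women only, with enrollment hemoglobin.* A true difference of 1.0 between arms is recovered as 0.99 to 1.01, with 95% CI coverage of about 95%.

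**The case against.** The strongest reply is that the bias is conditional on a reading. The documents also use the phrase iron supplementation for the randomised regimen: the title does so, and so does Study Design ("and a ferritin of less than 15mg/dL will be randomized to once or twice daily iron supplementation"). No aim asks about iron versus no iron. On that reading the term is already once versus twice, and the defect is ambiguity. This stands in part. Inclusion of the controls is inferred from the three-arm ANOVA and from the absence of any restriction. A reader might infer that the plan commits itself to an iron-versus-none coefficient, and the text does not go that far. Nor does it rule one out, and an analyst could follow it exactly and produce one.

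Four further points stand and limit the claim:
- Keeping the controls does not by itself damage the randomised contrast; a three-level factor leaves it unbiased.
- The ferritin adjustment does some work. Under the assumed distribution about 20% of controls have ferritin below 15, so the groups overlap on that variable. The uncorrected part runs through enrollment hemoglobin.
- It would be too strong to say that no adjustment can help. Adding enrollment hemoglobin removes the bias if a straight line holds across groups that hardly overlap on it: with one cut-off they do not overlap, and with cut-offs of 10.5 and 11 they can do so only within that band.
- The model is described as exploratory, and the sample size is unaffected.

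**Conclusion.** The concern holds in conditional form. If the controls enter and supplementation is coded yes/no or by dose, the planned covariates leave the hemoglobin coefficient confounded by indication and biased against iron. A true +1.0 is estimated at about -0.4 to +0.6.

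The starting gap of 1.8 to 2.1 follows from the plan's own mean, SD and cut-offs. The tracking, the correlations and the ferritin distribution are assumptions. Underestimation appeared in every cell examined.

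Two stronger readings are not supported. One is that the sign always reverses: for a true +1.0 many cells remain positive, and even for a true +0.5 some cells are slightly positive (+0.05 and +0.11). The other is that the cord results are biased by a similar amount. They may share the confounding, but its size was not computed, and the plan adjusts for maternal ferritin and hepcidin, which correspond to two of the three fetal outcomes. The randomised once-versus-twice contrast is not itself compromised. The change should be made, but the trial's design does not depend on it.

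**What to change.** Replace the regression sentence with:

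> Regression will be fitted in randomised women only, with arm (twice v once daily) as the term of interest, for maternal hemoglobin at delivery and for fetal hemoglobin, hepcidin and ferritin, adjusting for maternal hemoglobin, ferritin and hepcidin at enrollment. Controls will be summarised by means and 95% CIs, and no adjusted effect of supplementation v none will be interpreted causally.

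This ties the model to the frequency question in Aim 4, names the missing covariate and keeps all the outcomes now listed.

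The cost is wording only. About 200 controls leave the model, which loses little because they carry no direct information on once versus twice. With 40 randomised women remaining (50 less 20%), the adjusted model has 40 - 5 = 35 residual degrees of freedom. In the simulations with b of 0.5 or 0.7, it detected a true difference of 1.0 between arms in 92% to 99% of trials.

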In addition to routine standard of care blood draws, subjects will have two extra samples of blood taken for research use at no cost to them. The first will be drawn at the time of enrollment, generally at the time of a clinically indicated blood draw for routine prenatal labs. The second will be drawn at the time of admission to the hospital for delivery or on post partum day 1, again generally at the time of an otherwise clinically indicated blood draw. At this time, a separate tube of about 10mL will be drawn for research purposes only. A sample of cord blood from the placenta will be obtained following delivery of the neonate as well. These samples will be stored for analysis of hepcidin and ferritin at the conclusion of the study. These values will be for research use only and will not be used in clinical care.

Subjects will be administered a validated questionnaire regarding gastrointestinal (GI) symptoms of iron usage at the time of follow up clinic visits [5]. This questionnaire will be administered via RedCap or via paper per patient preference. Compliance will be monitored by having the patient bring pill packs to her clinic visits.

Whether or not the patient required a blood transfusion in the peripartum period will be recorded. Due to the relative infrequency of this outcome, this will be evaluated as a planned secondary outcome with the understanding that the trial will not be powered specifically for this outcome.

All samples collected will be collected for, stored, and processed by the MU Biorepository. Following study related analysis, the MU Biorepository will de-identify what is left of the samples and store the excess for future non-specified research endeavors.

Risks and Benefits

1. Iron therapy is associated with mild gastrointestinal symptoms (upset stomach and diarrhea). Increased iron dosage may be associated with an increased risk of these symptoms. Significant gastrointestinal symptoms are rare with once or twice daily iron dosage. The additional iron in maternal diet (which is classically iron poor in the US) or in prenatal vitamins will not pose any additional maternal risk. There is no fetal risk to this study.
2. There are no individual benefits to enrollment in the study.

Subject withdrawal criteria and procedures specifying

- When and how to withdraw subjects from the trial / investigational product treatment.
If subjects are not compliant with the tasks required in the protocol.

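### The regression lists fetal hemoglobin without a described measurement, and its wording leaves unclear whether follow-up maternal hepcidin (Specific Aim 3) is analysed

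*Combined protocol and SAP*

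**What the plan says.** The Data Analysis section contains one regression sentence. It relates iron supplementation to maternal hemoglobin at delivery and to "fetal hemoglobin, hepcidin, and ferritin while controlling for maternal ferritin and hepcidin at enrollment". The section names two other methods: ANOVA for mean hemoglobin at admission and post-partum, and a chi-square or Fisher test for blood transfusion.

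The measurements are described under Study Design:

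- Fetal material: "A sample of cord blood from the placenta will be obtained following delivery of the neonate as well".
- Assays on the research samples, maternal and cord: "These samples will be stored for analysis of hepcidin and ferritin at the conclusion of the study".
- Maternal research samples: one at enrollment, and a later one. "The second will be drawn at the time of admission to the hospital for delivery or on post partum day 1".
- Follow-up hemoglobin: "the subject will have a hemoglobin repeated at the time of admission to labor and delivery and on post-partum day 1".

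Two of the Specific Aims bear on this. Aim 3 is "Determine the relationship between frequency of maternal iron administration and maternal hepcidin". Aim 4 is "Determine the relationship between frequency of maternal iron administration and fetal iron stores".

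**The concern.** A plan should allow each listed outcome to be traced back to a measurement, and each aim forward to an analysis. The regression sentence raises a doubt in both directions. It lists fetal hemoglobin, which is not among the assays described. It also uses maternal hepcidin by name only as an enrollment covariate, while Aim 3 makes maternal hepcidin a quantity of interest.

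Hepcidin matters here beyond its place in a list of aims. The Summary gives it as the mechanism that may limit twice-daily dosing, and the section on anticipated results bases its expectation for once-daily dosing on it. If the outcome, contrast and covariates for maternal hepcidin are not fixed in advance, they may be chosen after the assays are run. The open choices would include absolute level or change, and two arms or three.

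**Working it through.** The point is one of traceability, so the check sets the sections side by side.

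**Plan's own figure.** The only figure that can be recomputed is the 17 subjects per arm in the Power Analysis, for a difference of 1 with standard deviation 1 (units as printed), alpha 0.05 and 80% power. The normal approximation gives n = 2 × (1.960 + 0.842)² × 1² / 1² = 15.7, so 16 per arm. The two-sample t-test gives 16.71, so 17 per arm, with power 80.7% at 17. The figure reproduces. It concerns maternal hemoglobin and does not depend on this point.

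**Step 1: from each possible outcome to a measurement.**

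| Quantity | Source described under Study Design |
|---|---|
| Maternal hemoglobin at delivery | Yes, routine care |
| Follow-up maternal hepcidin | Yes, second maternal research sample |
| Cord hepcidin and ferritin | Yes, cord sample |
| Fetal hemoglobin | None in the readable text |

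**Step 2: what the regression sentence can mean.** Three readings of hepcidin and ferritin are possible.

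| Reading | Fetal hemoglobin | Follow-up maternal hepcidin (Aim 3) | Cord hepcidin and ferritin (Aim 4) |
|---|---|---|---|
| A. The word fetal governs all three nouns | No described source | No stated analysis | Analysed |
| B. Hepcidin and ferritin are maternal only | No described source | Analysed | No stated analysis |
| C. Hepcidin and ferritin are both maternal and cord | No described source | Analysed | Analysed |

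Reading A is the most natural grammatically and fits Aim 4. Under B, Aim 4 would rest on fetal hemoglobin alone, which has no described source. Only C serves both aims, and it needs the same two words to stand for two sets of samples, which the sentence does not say.

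**Step 3: do the other analyses fill the gap?** No. The ANOVA is for hemoglobin and the chi-square or Fisher test is for transfusion. Neither names hepcidin.

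**Step 4: covariates.** The regression adjusts for enrollment ferritin and hepcidin. It does not adjust for enrollment hemoglobin when hemoglobin is the outcome, although a hemoglobin value is needed to establish eligibility for randomization and is therefore already available.

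**The case against.** The strongest reply is that the sentence is loose rather than silent. It can be read as maternal and fetal hemoglobin, followed by hepcidin and ferritin in every sample assayed. The context gives some support: the maternal and cord samples are stored together for the same two assays, adjusting for enrollment hepcidin is natural if later maternal hepcidin is an outcome, and Aim 3 names it. This stands in part. The Aim 3 gap depends on how the sentence is read, and the fair description is ambiguity. It does not help fetal hemoglobin, which lacks a described source on all three readings.

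The reply can add that the consequence is limited. The regression is exploratory in purpose, and neither hepcidin nor fetal hemoglobin is named as a primary or secondary outcome in the Summary. That also stands.

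A reader might infer several stronger things that the documents do not support:

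- That fetal hemoglobin could never be recovered from stored cord blood. The protocol does not say in what form the cord blood is kept.
- That no randomized pregnancy will have the value. The Study Design figure is not shown and could list a test. What can be said is that no readable section does.
- That Aim 3 is the only aim without a named analysis. No test is named for gastrointestinal symptoms (Aim 2) either, so a count of one aim in four would be wrong.
- That data for Aim 3 are lost. The second maternal sample is planned and is to be assayed for hepcidin. At most, the stated analysis is missing.

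**Conclusion.** The point holds in two parts of different strength. First, fetal hemoglobin is a listed regression outcome with no measurement described in the readable text. This is so on every reading and rests only on the assumption that the missing figure does not supply one. Second, the sentence does not say whose hepcidin and ferritin it means. On the most natural of three readings, follow-up maternal hepcidin is an outcome of no stated analysis; on the other two it is covered.

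The size is modest: one outcome without a described source, and one aim whose analysis is uncertain. A reader might take this as a threat to the main result. It is not, because the primary ANOVA on maternal hemoglobin and the 17 per arm behind it do not use either quantity. It should still be corrected, because hepcidin is the trial's proposed mechanism and the correction is small.

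**What to change.** Before unblinding, make two changes to the regression sentence.

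1. Either delete fetal hemoglobin, or specify under Study Design that a hemoglobin is measured on the cord sample at collection from now on, and report values from earlier deliveries as missing. The protocol is at Version 8 and does not say whether any participant has already delivered, so the change should not assume that none has.
2. Name the outcomes, the contrast and the covariates. For example:

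> Regression will compare once with twice daily iron for maternal hemoglobin at delivery (Aim 1), maternal hepcidin in the second research sample (Aim 3), and cord hepcidin and cord ferritin (Aim 4). All models adjust for enrollment ferritin and hepcidin; the hemoglobin model also adjusts for enrollment hemoglobin.

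This keeps the covariates already planned and adds one that is collected at screening. The cost is one revised sentence and, if fetal hemoglobin is kept, one extra assay on a sample already taken. It needs no further blood draws or subjects and no change to treatment, the primary ANOVA or the sample size.

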Project Title: Once Daily versus Twice Daily Iron Supplementation to Treat Anemia in Pregnancy: A Prospective, Randomized, Placebo Controlled, Double Blinded, Clinical Trial

IRB#: 2004638

Version 8, September 24, 2019

Principle Investigator:

[name]

Assistant Professor, Department of Obstetrics and Gynecology
[name]

Summary

Anemia is a common problem in pregnancy, affecting as many as 1/4 of pregnancies in the developed world in the absence of iron supplementation. It is defined as a maternal hemoglobin (Hgb) less than 11mg/dL in the 1st or 3rd trimester and Hgb less than 10.5mg/dL in the 2nd trimester [1].. Anemia is associated with low birth weight, preterm birth, and increased risk for transfusion at the time of delivery [1]. The most common cause of anemia in pregnancy is iron deficiency. Iron deficiency anemia in pregnancy is typically treated with oral iron supplementation in the form of once or twice daily ferrous sulfate, which contains 65mg of elemental iron.

Iron balance is complex, and iron demands are increased in pregnancy. The fetus, placenta, and increased maternal red blood cell volume require about 1g of additional iron during the entire pregnancy. The average American diet contains only about 15mg of elemental iron, which is insufficient to meet this need[1]. It is recommended that pregnant women consume about double this amount during pregnancy[1].

The absorption of oral iron is low, ranging from 2-28%. Taking iron without food increases absorption. Hepcidin is a key regulator of iron absorption in mammals, increasing hepcidin decreases iron absorption. Hepcidin is increased with morning fasting dosing, which may affect the efficacy of twice daily dosing (Morretti). Well-designed clinical trials describing the optimal dosing for iron to treat anemia in pregnancy are limited [2, 3].

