A recent publication by Morretti et al [4] evaluated the effect of different doses of oral iron in non-pregnant iron deficient young women. They evaluated the effect of varying doses of daily ferrous sulfate and once and twice daily dosing of ferrous sulfate on hepcidin levels and fractional and total iron absorption. Women were treated with a single daily dose ranging from 40-240mg of elemental iron. This 6-fold increase in elemental iron dosage only resulted in a 3 fold increase in the amount of elemental iron absorbed, contradicting the notion that more iron is better. In a second arm of the study, women were treated with twice daily dosing for a total of 180mg of elemental iron. **The results of the study demonstrated that 24 hours after a dose > 60mg, hepcidin increased and fractional iron absorption decreased by 35-45%. Multiple daily doses did not increase iron absorption beyond single daily dosing.** The authors concluded that providing daily dosages less than 80mg of elemental iron and avoiding

twice daily dosing maximized iron absorption. **The results of the study by Morretti et al challenge the conventional wisdom that more severe iron deficiency anemia in pregnancy is best treated by increasing from daily to twice daily supplementation. Morretti et al also did not evaluate for gastrointestinal side effects or increase in hemoglobin.**

Given the high incidence of iron deficiency anemia in pregnancy and the associated complications, we propose a prospective, randomized double blinded clinical trial to evaluate the optimal dosing of oral iron supplementation in pregnancy. We will recruit mothers identified as having iron deficiency anemia at the time of routine prenatal blood work in the second trimester. These subjects will be randomized to daily or twice daily ferrous sulfate 325mg (65mg of elemental iron). The primary outcomes will be hemoglobin concentration at the time of admission for delivery and post-partum and assessment of gastrointestinal side effects. The secondary outcome will be frequency of blood transfusion at the time of delivery.

Hypothesis: Once daily dosing of ferrous sulfate 325mg/dL will be associated with increased maternal hemoglobin concentration at the time of delivery and post-partum and decreased gastrointestinal side effects.

Specific Aims

1. Determine whether once daily dosing of oral iron is more effective in raising maternal Hgb concentration than twice daily dosing.

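### Enrolment hemoglobin and gestational age are left out of the planned hemoglobin analyses; pre-specifying them is a cheap, optional precision measure whose gain may be small or nil

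*Combined protocol and SAP*

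**What the plan says.** - **Aim and outcomes.** The first of the Specific Aims asks whether once-daily iron is "more effective in raising maternal Hgb concentration than twice daily dosing". The Summary states: "The primary outcomes will be hemoglobin concentration at the time of admission for delivery and post-partum", alongside gastrointestinal side effects.
- **Main hemoglobin analysis.** Under Data Analysis, Statistical Analysis, an ANOVA assesses the "difference in mean hemoglobin at the time of admission and post-partum in the three arms". No covariate is named.
- **Regression.** The same paragraph adds: "Regression analysis will be used to explore the relationships of iron supplementation on maternal hemoglobin at delivery", together with fetal measures, "while controlling for maternal ferritin and hepcidin at enrollment". Enrolment hemoglobin and gestational age are not listed, and post-partum maternal hemoglobin is not among the regression outcomes.
- **What is known at entry.** Inclusion Criteria limit enrolment to 14 to 28 weeks. Study Design defines who is randomised: "Subjects with iron deficiency anemia as diagnosed by an Hgb concentration of less than 10.5-11mg/dL", plus a ferritin limit. The Summary gives the trimester-specific threshold as "Hgb less than 10.5mg/dL in the 2nd trimester". Hepcidin, by contrast, is assayed from stored samples when the study ends.
- **Power Analysis.** One reason given for randomising 50 women is to leave room for covariate adjustment, but that section does not say which covariates.

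**The concern.** Aim 1 is about a rise in hemoglobin, yet the ANOVA compares final values alone and the regression adjusts for two iron markers but not for the starting value of the outcome. Enrolment spans 14 weeks, so two women delivering at the same gestation can differ by up to 14 weeks in time on iron. No stratification is described, so with about 20 women per arm the arms may differ by chance in starting hemoglobin or enrolment timing.

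None of this biases a randomised comparison. At stake are the width of the confidence interval for the main comparison, and whether covariates are named before or after the data are seen. The second benefit does not depend on how well the covariates predict.

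**Working it through.** **Inputs from the Power Analysis:** alpha 0.05 (two-sided assumed, since that reproduces the stated size), difference 1, SD about 1, mean about 12, 50 randomised equally, 20% attrition, about 200 controls. Hence 25 × 0.8 = 20 evaluable per arm and 200 × 0.8 = 160 controls (same attrition assumed).

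**Not in the documents:** R, the joint correlation of the two covariates with hemoglobin at delivery. A range is shown.

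**1. The plan's own figure.** Two-sample t-test, noncentral t: 16 per arm gives 78.1% power and 17 gives 80.7%. The stated 17 reproduces.

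**2. Adjusted analysis.** With k = 2 covariates,

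variance = SD² × (2/n) × (1 − R²) × [1 + k/(2n − k − 3)], with df = 2n − 2 − k.

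At n = 20 the inflation term is 1 + 2/35 = 1.057 and df = 36.

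| Analysis (n = 20 per arm, SD 1) | Power | 95% CI half-width |
|---|---|---|
| Unadjusted two-arm t-test (df 38) | 86.9% | 0.64 |
| Contrast from three-group ANOVA (df 197) | 88.2% | 0.62 |
| Adjusted, R = 0 | 84.9% | 0.66 |
| Adjusted, R = 0.2 | 86.3% | 0.65 |
| Adjusted, R = 0.4 | 90.4% | 0.60 |
| Adjusted, R = 0.6 | 96.2% | 0.53 |

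Against the t-test, break-even is R = 0.238 and the worst loss is 86.9 − 84.9 = 2.0 points. Against the three-group contrast, break-even is R = 0.309 and the worst loss 88.2 − 84.9 = 3.3 points; this comparator assumes a common variance in anemic women and controls and no multiplicity correction. Against the t-test, break-even is 0.262 at 17 per arm and 0.210 at 25 per arm.

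**3. Effect of the entry cut-off.** Suppose instead that mean 12 and SD 1 describe pregnant women in general (normal), entry truncates hemoglobin from above, and only hemoglobin predicts. The SD of enrolment hemoglobin becomes u = 0.387 (cut-off 10.5) or 0.446 (cut-off 11). For an unrestricted correlation r,

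outcome SD = √(1 − r² + r²u²), and restricted R = r × u / outcome SD.

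| Cut-off | r | Outcome SD | Restricted R | Power, unadjusted → adjusted |
|---|---|---|---|---|
| 10.5 | 0.3 | 0.961 | 0.121 | 89.4% → 88.0% |
| 10.5 | 0.5 | 0.887 | 0.218 | 93.5% → 93.3% |
| 10.5 | 0.7 | 0.764 | 0.354 | 98.1% → 98.7% |
| 11 | 0.3 | 0.963 | 0.139 | 89.2% → 88.0% |
| 11 | 0.5 | 0.894 | 0.249 | 93.1% → 93.3% |
| 11 | 0.7 | 0.779 | 0.401 | 97.7% → 98.7% |

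From unrounded powers the change runs from -1.3 to +1.0 points. Break-even needs an unrestricted r of about 0.54 (cut-off 10.5) or 0.48 (cut-off 11). Simulation with 20,000 runs per cell agrees to within 0.3 points. The ferritin limit could narrow the range further.

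**4. Gestational age alone.** If enrolment is uniform over 14 to 28 weeks, its SD is 14/√12 = 4.04 weeks. With outcome SD 1, R = 0.238 requires a slope of 0.238/4.04 = 0.059 per week, or about 0.82 over 14 weeks. R = 0.309 requires 0.309/4.04 = 0.0765 per week, or 0.0765 × 14 = 1.07.

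**5. Adding enrolment hemoglobin to ferritin and hepcidin.** For a third covariate in the two randomised arms (20 each), break-even is a partial correlation of about 0.17. If it is zero, power falls from 84.9% to 83.8% (existing covariates uninformative) or from 90.4% to 89.5% (existing R = 0.4), about 1 point.

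**The case against.** The strongest reply is that nothing here needs curing. The planned comparison is valid, the sample size reproduces, and 20 per arm already gives 86.9%. The deciding quantity, R, is nowhere in the protocol. The scenario closest to the protocol's own figures (cut-off 10.5) gives -1.3, -0.2 and +0.6 points for r of 0.3, 0.5 and 0.7. For gestational age to break even alone, the slope would have to amount to 0.82 over the enrolment window, most of the target difference of 1, and more per week if enrolment clusters around routine blood work. The regression already adjusts for two baseline iron markers. Making ANCOVA the main estimate is also more than a wording change.

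Most of this stands as a limit on the expected gain, and it is why the point is optional. The 90.4% and 96.2% figures should not be read as forecasts. The 3.3-point loss rests on a common variance that the truncation scenario would contradict, so it is an upper figure.

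It does not remove the point. The truncation scenario gives gestational age no predictive value, so it does not bound the joint gain. The regression is worded as exploratory, omits both variables and does not cover post-partum maternal hemoglobin. The Power Analysis anticipates adjustment without naming covariates, so the main comparison has none fixed in advance. The remedy does change which number leads, and the sponsor should accept that knowingly.

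**Conclusion.** The point holds as an optional improvement in precision, not as a flaw. Two baseline variables that every randomised woman has are absent from both hemoglobin analyses. With 20 evaluable per arm and SD 1, adjusting for them moves power from 86.9% to between 84.9% (R = 0) and 96.2% (R = 0.6). The possible loss is bounded at about 2 points against a two-arm t-test, or 3.3 against a three-group contrast. Because eligibility restricts enrolment hemoglobin, that variable may contribute little or nothing; any larger gain would need gestational age, or a stronger correlation than the documents support. These figures assume two-sided testing, 20% attrition, normality and an R that the protocol does not supply. Confidence in the benefit is moderate at best. Fixing the covariates in advance is worthwhile whatever R turns out to be.

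**What to change.** Add to the Statistical Analysis section: *The once- versus twice-daily difference in hemoglobin, at admission and separately on post-partum day 1, will be estimated among randomised women by ANCOVA with terms for arm, enrolment hemoglobin and gestational age at enrolment (both continuous). The adjusted difference and its 95% confidence interval will be reported, with the unadjusted difference as a sensitivity analysis.*

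Keep the three-group ANOVA as a separate descriptive comparison, since the controls are neither randomised nor anemic and differ in enrolment hemoglobin by design. Add enrolment hemoglobin to ferritin and hepcidin in the maternal-hemoglobin regression.

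The cost is a short paragraph, with no extra data, visits or women. The price is two degrees of freedom in the main comparison, the bounded power loss above if the covariates are uninformative, and a change in which estimate is presented first.
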